#### 4.10.1.2. Safety Subgroups

The summary of exposure to study medication will be summarized by the following subgroups: Age 1 and Sex, Race 1, and Region 2.

The summary of overview of all on-treatment AEs will be summarized by the Region 2 subgroup.

The summary table of on-treatment AEs by SOC and PT will be summarized by the following subgroups: Age 1, Age 2, Sex, Race 1, Region 1, and Region 2.

For the subgroups related to age, if there are no subjects within a particular age category (i.e. 12-17), then that age category will not be displayed.

# 4.11. Interim Analyses

No interim analyses of efficacy data are planned.

An independent data monitoring committee (IDMC) periodically reviewed unblinded safety data from this study and ANCHOR-2.

## 4.12. Changes to Protocol Defined Analyses

There were no changes or deviations to the originally planned statistical analysis specified in the protocol.

# 5. SAMPLE SIZE DETERMINATION

The sample size for this study is based on the co-primary efficacy endpoints of total endoscopic nasal polyps score at Week 52 and mean nasal obstruction VRS symptoms score from Week 49 through to Week 52, and a pre-specified pooled analysis of data from study ANCHOR-1 (this study) and ANCHOR-2 for the key secondary endpoint of time to first nasal surgery (actual or entry on waiting list) ) or disease-modulating medication for CRSwNP.

Approximately 250 participants were planned to be randomized in this study in a ratio of 1:1 giving 125 randomized participants per arm. This sample size allows for up to 5% of randomized participants to be non-evaluable, providing a minimum of 118 evaluable participants per arm in the analyses of primary and secondary endpoints.

For the co-primary efficacy endpoint of total endoscopic nasal polyps score at Week 52, the study has >99% power assuming a true population difference of -1.10 between depending and placebo. This assumes a standard deviation of 1.665 with significance declared at the two-sided 5% significance level. The smallest observed effect which is predicted to result in a statistically significant difference between depending 100 mg SC + SoC and placebo + SoC is a treatment difference of -0.42.

For the co-primary efficacy endpoint of mean nasal obstruction VRS score during Weeks 49-52, the study has >99% power assuming a true population difference of -0.70 between depending and placebo. This assumes a standard deviation of 0.84 with significance declared at the two-sided 5% significance level. The smallest observed effect which is predicted to result in a statistically significant difference between depending by 100 mg SC + SoC and placebo + SoC is a treatment difference of -0.21.

The overall power for both co-primary endpoints is >99%.

The planned number of patients recruited within this study is not sufficient to adequately assess whether depemokimab significantly reduces the risk of nasal surgery compared to placebo. A pre-specified pooled analysis of data from this study (ANCHOR-1) and ANCHOR-2 is planned for the endpoint of time to requiring first nasal surgery (actual or

entry on waiting list) or disease-modulating medication for CRSwNP. The proportion of participants in the pooled placebo group expected to require surgery or disease-modulating medication for CRSwNP is 23%. Assuming a true population hazard ratio of 0.38 (62% reduction in risk of required surgery) this pooled analysis has >90% power to observe statistical significance at the 2-sided 4.75% level. In the pooled analysis, the smallest observed effect which is predicted to result in a statistically significant difference between depemokimab 100 mg SC + SoC and placebo + SoC is a hazard ratio of 0.64 (36% reduction in risk of surgery).

The overall power for both co-primary endpoints and the pre-specified pooled analysis of time to requiring first nasal surgery (actual or entry on waiting list) or disease-modulating medication for CRSwNP using data from this study (ANCHOR-1) and ANCHOR-2 is >90%.

## 6. SUPPORTING DOCUMENTATION

# 6.1. Appendix 1 Study Population Analyses

The study population analyses will be based on the FAS, unless otherwise specified.

Study population analyses including analyses of participant's disposition, protocol deviations, demographic and baseline characteristics, prior and concomitant medications, and study treatment compliance will be based on GSK Core Data Standards.

## 6.1.1. Participant Disposition

Summary tables showing the reasons for screen failure and run-in failure will be provided using the Screened Analysis set.

A summary of participant status and reason for study withdrawal will be provided. This display will show the number and percentage of participants who completed the study and who withdrew from the study, including the primary reason for study withdrawal. A participant is considered to have completed the study if they complete the Week 52 visit.

A summary of study treatment status will be provided. This display will show the number and percentage of participants who have completed the scheduled study treatment or have discontinued study treatment prematurely and a summary of the primary reason for discontinuation of study treatment.

A summary of the number of participants in each of the analysis sets describe in Section 3, along with the number of participants randomized will be provided using the Screened Analysis Set.

The number of participants randomized to each strata and number of participants with each actual strata (in cases of incorrect strata allocation) will also be summarized.

The number of participants enrolled by region, country and center will be summarized.

# 6.1.2. Demographic and Baseline Characteristics

The demographic characteristics (e.g., sex, age, ethnicity, race, region, height, weight and derived BMI) will be summarized by descriptive statistics. An additional summary of age ranges using the EMA clinical trial results disclosure requirement categories will be produced and is based on the Enrolled Analysis Set. If the summary of demographics meets the criteria for de-identification, as described in the relevant procedural document, a de-identified version should be produced.

Summaries of disease history and characteristics will be provided. Tables will include duration of chronic rhinosinusitis, duration of nasal polyps, history of nasal polyps surgery prior to screening, history of systemic corticosteroid use for nasal polyps, baseline blood eosinophils count, total Immunoglobulin E (IgE), intranasal corticosteroid (INCS) use at baseline, and aspirin-exacerbated respiratory disease (AERD) at baseline.

Summary statistics for the baseline values of efficacy and safety endpoints will be included in the efficacy and safety summary tables for those endpoints respectively. Additionally, a summary table for the baseline efficacy for the co-primary and secondary endpoints within the hierarchy will be summarized by treatment group and overall.

Additionally, asthma status, asthma exacerbation history in the 12 months prior to screening, ACQ-5 score at baseline, and tobacco history will also be summarized.

Medical conditions collected at screening will be summarized for current and past conditions separately.

#### 6.1.3. Protocol Deviations

Important protocol deviations will be summarized.

Protocol deviations will be tracked by the study team throughout the conduct of the study. These protocol deviations will be reviewed to identify those considered as important as follows:

- Data will be reviewed prior to unblinding and freezing the database to ensure all important deviations (where possible without knowing the study intervention details) are captured and categorized in the protocol deviations dataset.
- This dataset will be the basis for the summaries of important protocol deviations.

#### 6.1.4. Prior and Concomitant Medications

Concomitant medications (CM) will be coded using the WHO Drug dictionaries. Summaries of the number and percentage of participants taking concomitant medications will be displayed by ingredient only (not by ATC classification). These summaries will include single-ingredient medications and will present multi-ingredient medications according to the combination of the component ingredients. Separate summaries will be produced for those medications taken pre-, during, and post-treatment.

**Pre-Treatment:** CM Start Date < Study Treatment Start Date

**On-Treatment (During):** If CM Start Date < Study Treatment Start Date and CM Stop Date >= Study Treatment Start Date

Or

If Study Treatment Start Date < CM Start Date < Last Dose of Study Treatment Date + 182 days

**Post-Treatment:** If CM Start Date < Last Dose of Study Treatment Date + 182 days

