# 6.3.2. Study Period

Assessments and events will be classified according to the time of occurrence relative to the study intervention period.

**Pre-treatment** is defined as time prior to the first dose of study intervention.

Assessment/Event Date ≤ Study Treatment Start Date

**On-treatment** is defined as time from first dose to last date plus 182 days.

Study Treatment Start Date < Assessment/Event Date ≤ Date of Last Dose of Study Treatment + 182 days

**Post-treatment** is defined as any time post on-intervention window, i.e. > last dose date plus 182 days.

Assessment/Event Date > Date of Last Dose of Study Treatment + 182 days

Assessments collected on the date of randomization, for which there is no time of assessment will be considered pre-intervention.

Assessments will be considered on-treatment if the assessment start date is missing.

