# 6.3.6. Handling of Partial Dates

Element	Reporting Detail		
General	
 
Partial dates we displays.
 
However, whe temporary varidates may be specific analys.
 
Imputed partial onset or duration or elapsed time imputed dates.
 
	re necessary, display macros may impute dates as ables for sorting data in listings only. In addition, partial imputed for 'slotting' data to study phases or for its purposes as outlined below.  I dates will not be used to derive study day, time to on (e.g., time to onset or duration of adverse events), e variables (e.g., time since diagnosis). In addition, are not used for deriving the last contact date in I analysis dataset.	
Adverse Events		or AE recorded in the CRF will be imputed using the	
	Missing start day and month	If study intervention start date is missing (i.e. participant did not start study intervention), then set start date = January 1.  Else if study intervention start date is not missing:  If year of start date = year of study intervention start date, then  If stop date contains a full date and stop date is earlier than study intervention start date, then set start date = January 1.  Else set start date = study intervention start date.  Else set start date = January 1.	
	Missing end day  Missing end day and month	A '28/29/30/31' will be used for the day (dependent on the month and year).  No Imputation	

Element	Reporting Detail		
	Completely	No imputation	
	missing	'	
	start/end date		
Concomitant Medications/Medical		for any concomitant medications recorded in the CRF ed using the following convention:	
History	Missing start day	If study intervention start date is missing (i.e. participant did not start study intervention), then set start date = 1st of month.  Else if study intervention start date is not missing:  If month and year of start date = month and year of study intervention start date, then  If stop date contains a full date and stop date is earlier than study intervention start date, then set start date = 1st of month.  Else set start date = study intervention start date.	

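### SAP 6.1.4 prints the post-treatment medication rule with its inequality reversed, so the three medication-period summaries overlap, omit late starts and misplace the first-dose day

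*SAP*

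**What the plan says.** SAP 6.1.4 commits to three tables: "Separate summaries will be produced for those medications taken pre-, during, and post-treatment". The rules are:

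- Pre-treatment: "CM Start Date < Study Treatment Start Date".
- On-treatment, first branch: "If CM Start Date < Study Treatment Start Date and CM Stop Date >= Study Treatment Start Date".
- On-treatment, second branch: "If Study Treatment Start Date < CM Start Date < Last Dose of Study Treatment Date + 182 days".
- The third table, meant for medications after the treatment window, has this rule: "If CM Start Date < Last Dose of Study Treatment Date + 182 days".

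SAP 6.3.2 sets the general study periods. On-treatment is "Study Treatment Start Date < Assessment/Event Date ≤ Date of Last Dose of Study Treatment + 182 days" and post-treatment is "Assessment/Event Date > Date of Last Dose of Study Treatment + 182 days". Its pre-treatment formula includes the treatment start date itself.

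SAP 6.3.6 imputes partial medication start dates. The start day may be missing in the month of first dose, or the day and month missing in the year of first dose. If no full stop date precedes first dose, the rule is then "Else set start date = study intervention start date".

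Concomitant medication review continues to the follow-up contact, 30 weeks after the last dose (Protocol 1.3, Table 1 and footnote e).

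**The concern.** The post-treatment rule has the same upper bound, in the same direction, as the second on-treatment branch. It therefore selects medications that started before the end of the treatment window, when the table exists to show those that started after it. It has no lower bound and no stop-date condition, so nothing keeps earlier medications out.

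A second weakness lies at the start of treatment. The pre-treatment rule and both on-treatment branches use strict inequalities at the treatment start date, so a medication begun that day satisfies none of them. The reversed post-treatment rule then picks it up.

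At stake is whether the medication tables can be read at all. A programmer who follows the SAP produces a post-treatment table made up of earlier medications. One who silently corrects it departs from the SAP without a record.

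**Working it through.** This is date logic, so there is no planned figure to reproduce.

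**Notation.** T = study treatment start date, L = last dose date, B = L + 182 days, s = medication start, e = medication stop.

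**Printed rules (SAP 6.1.4).**
- Pre: s < T.
- On: (s < T and e ≥ T) or (T < s < B).
- Post: s < B.

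**General periods (SAP 6.3.2).**
- Pre: date ≤ T.
- On: T < date ≤ B.
- Post: date > B.

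**Assumed nominal dates.**
- Two doses: T = Day 1, L = 1 + 182 = Day 183, B = 183 + 182 = Day 365.
- One dose: T = L = Day 1, B = 1 + 182 = Day 183.

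**Step 1: the printed rules applied to typical records.**

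| Medication | Two doses | One dose | Periods as printed |
|---|---|---|---|
| Stopped before dosing | Day −60 to −10 | Day −60 to −10 | pre and post |
| Started before dosing, ongoing | from Day −60 | from Day −60 | pre, on and post |
| Started on first-dose day | Day 1 | Day 1 | post only |
| Started the day after | Day 2 | Day 2 | on and post |
| Started at B − 1 | Day 364 | Day 182 | on and post |
| Started at B | Day 365 | Day 183 | none |
| Started at B + 20 | Day 385 | Day 203 | none |

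**Step 2: all start days.** The rules were applied to start days −100 to 420 (521 days), each with 14 stop dates plus ongoing use, giving 521 × 15 = 7,815 records per dosing case.
- Records on-treatment but not post-treatment: 0.
- Records pre-treatment but not post-treatment: 0.
- Start days in no period: 365 to 420 with two doses, 183 to 420 with one dose.
- Start days classified post-treatment only: Day 1 alone, in both cases.

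**Step 3: length of the uncovered stretch.**
- Two doses, or one dose with early withdrawal: the follow-up contact is 30 × 7 = 210 days after the last dose, and 210 − 182 = 28 days, or 4 weeks.
- One dose, staying to Week 52 as Protocol 7.1 encourages: Day 365 − Day 183 = 182 days, or 26 weeks. If the Week 56 contact also takes place, 56 × 7 − 182 = 210 days, or 30 weeks.

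**Step 4: would reversing the sign alone be enough?** With post set to s > B, the spurious overlap goes and late starts are captured. Two start days still have no period: T and B (Days 1 and 365 with two doses, Days 1 and 183 with one). With s ≥ B, only T is left out. The first-dose day therefore needs its own correction.

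**The case against.** **Reading error.** The text was read from PDF, and comparison signs are damaged elsewhere (the age categories in SAP Table 1). A ≤ misread as < could remove the first-dose-day result. It could not turn the post-treatment rule round, and starts after last dose + 182 days would still have no period. Other signs in 6.1.4 and 6.3.2 survive intact, so misreading is possible but unlikely. The first-dose-day result is the least certain of the three.

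**Intended overlap.** The summary concerns medications taken post-treatment, so one continuing past the window might be meant to appear there. That would need a stop-date condition, which is absent, and later starts would still be omitted. The objection does show that a rule based on start date alone may not meet the stated purpose.

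**Output may differ from the text.** SAP 6.1 says these displays follow the sponsor's data standards, which are not in the documents, so the printed rule may never reach a table. That is a reason to correct the SAP, not to leave it.

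**Stronger readings.** A reader might infer that the error reaches the primary analysis, because disease-modulating medication is a composite intercurrent event. The documents do not support this: SAP 4.2.1 assigns worst scores after the date of the first intercurrent event and does not use these periods. A reader might also infer that late medication data are lost. Protocol 6.8 requires every medication received during the study to be recorded, so the records exist but are missing from the summary. Nor do all partial start dates move to the first-dose day: the 6.3.6 rule applies only when the known month or year matches that of first dose and no full stop date precedes it.

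**Conclusion.** The printed rule is wrong, and SAP 6.1.4 contradicts SAP 6.3.2. All pre- and on-treatment medications are repeated as post-treatment. Starts on or after last dose + 182 days appear nowhere, which covers about 4 weeks of collection after two doses and about 26 weeks or more for one-dose participants who stay to Week 52. First-dose-day starts, including dates imputed to that day, appear only as post-treatment.

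The durations assume nominal dosing and contact dates. The first-dose-day result also assumes that the strict signs are as printed. The effect is confined to descriptive concomitant-medication summaries; no endpoint, estimand or test uses these periods. It should be corrected before the tables are produced.

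**What to change.** In SAP 6.1.4:

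1. Change the post-treatment rule to CM Start Date > Last Dose + 182 days.
2. Make the upper bound of the second on-treatment branch ≤ Last Dose + 182 days, as in 6.3.2.
3. Assign the first-dose day to one period and make 6.1.4 and 6.3.2 agree. Section 6.3.2 is itself divided: its wording starts the on-treatment period at first dose, while its formulas put that day in pre-treatment. If on-treatment is chosen, the lower bound of the second branch becomes ≤ and the two 6.3.2 formulas change to match. If pre-treatment is chosen, the pre-treatment rule becomes ≤, and the first on-treatment branch needs the same change so that a drug begun that day and continued still counts as on-treatment.
4. Decide whether medications continuing past last dose + 182 days count as taken post-treatment. If so, add a stop-date condition modelled on the first on-treatment branch.

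With items 1 and 2 and the on-treatment choice in item 3, every start date has a period, and the only overlap is pre-treatment medication still in use at first dose. Item 4 would add a deliberate second overlap.

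The cost with the on-treatment choice is three operators in 6.1.4, the first-dose-day reconciliation in 6.3.2 and the matching programming specification. No data collection changes.

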# 6.2. Appendix 2 Electronic Clinical Outcome Assessment (eCOA) Compliance

The compliance of eCOA data (e.g., assessments collected via electronic patient diary cards) will be derived at the study-level (overall) and at the endpoint-level across all participants and by treatment group.

An eCOA will be considered complete if there is no missing data within the assessment.

# 6.2.1. Study-Level (Overall) Compliance

The study-level (overall) compliance for all eCOA assessments collected in the study will be assessed for all participants at all time-points between baseline through to the date of the participant's study completion or withdrawal. If an eCOA is only assessed for a certain sub-population, the compliance for only that sub-population will be included in the compliance calculation (i.e. ACQ-5 only administered in participants with asthma). The list of eCOA assessments that comprise the study-level (overall) compliance include all eCOA assessments collected within the study: VRS, VAS, Nasal Obstruction VAS, SNOT-22, PGIS, PGIC, ACQ-5, SF-36, and WPAI-GH.

The analyses related to the ACQ-5 endpoint are described in the pooled SAP, but are included in the compliance metrics for completeness.

The target overall compliance for the study is 70%.

Overall eCOA compliance (across all eCOAs and all participants) for the study is calculated as:

 $\frac{\textit{Total number of complete eCOAs across all participants}}{\textit{Total expected number of complete eCOAs across all participants}} \times 100$ 

Expected number of complete eCOAs

$$= \sum_{i=1}^{n} \sum_{j=1}^{c} data \ points \ expected \ for \ eCOA_{j}(participant \ i)$$

where *c* represents the total number of eCOAs collected and *n* represents the total number of participants.

For daily diary data this means every day is a data point in the denominator. For visit-based endpoints, each visit is a data point in the denominator. The study-level (overall) compliance metric will be summarized by treatment group and total across treatment groups.

A supplemental overall compliance metric will also be calculated for the study. The supplemental calculation will be based on an interval-based definition for daily diary data that is defined within Section 6.3.4.2 for a four-week interval result to be non-missing in the analysis. The number of data points in the denominator for the interval-based definition becomes the number of four-week time periods that are assessed, including the baseline assessment. Participants are considered compliant for the daily diary endpoints if the appropriate number of non-missing values for each interval per the criteria described in Section 6.3.4.2. The denominator for the visit-based endpoints will remain the same. For visit-based endpoints, participants are considered compliant if they complete the assessment at that visit. This calculation will only include the eCOA endpoints in the multiplicity hierarchy: VRS, SNOT-22, and ACQ-5.

Both the study-level compliance and the supplemental overall compliance will be summarized at the participant level by pre-defined ranges for compliance (<40%, 40-<60%, 60-<80%>=80%). These will be summarized by treatment group and total across treatment groups.

## 6.2.2. Endpoint-Level Compliance

The daily eCOA assessments will be assigned a single four-weekly analysis time point as detailed within Section 6.3.4.2. Participants are considered compliant if the appropriate number of non-missing values for each interval per the criteria described in Section 6.3.4.2.

All visit-based eCOA assessments will be assigned analysis time points as detailed within Section 6.3.4.1. Participants are considered compliant if they complete the assessment at that visit.

The compliance for all eCOA endpoints in the multiplicity hierarchy (VRS, SNOT-22, ACQ-5) will be reported for each analysis time point by treatment group and total across treatment groups.

